# Table 4 (Table 2) – Ventilation and Intraoperative Characteristics

|   | Individualized
High PEEP
( n = XXX) | Low PEEP
(n = XXX) | Absolute Difference
(95% Cl) | p value |
|---|--|-----------------------|---------------------------------|----------------|
| Mean arterial pressure, mmHg                    | . ,  |                       |                                 |                |
| After intubation                                |  |                       |                                 |                |
| During first hour                               |  |                       |                                 |                |
| Last hour                                       |  |                       |                                 |                |
| Duration of anesthesia, min                     |  |                       |                                 |                |
| Duration of surgery, min                        |  |                       |                                 |                |
| Duration of surgery ≥ 180 min – no. (%)         |  |                       |                                 |                |
| Maintenance of anesthesia – no. (%)
Volatile |  |                       |                                 |                |
|   |  |                       |                                 |                |
| Epidural – no. (%)                              |  |                       |                                 |                |
| Thoracic  |  |                       |                                 |                |
| Lumbar  |  |                       |                                 |                |
| Neuromuscular monitoring – no. (%)              |  |                       |                                 |                |
| Residual paralysis at extubation– no. (%)       |  |                       |                                 |                |
| Paralysis reverted – no. (%)                    |  |                       |                                 |                |
| Temperature at the end of the surgery, °C       |  |                       |                                 |                |
| Fluids  |  |                       |                                 |                |
| Total intake, mL                                |  |                       |                                 |                |
| Crystalloids intake, mL                         |  |                       |                                 |                |
| Colloid – no. (%)                               |  |                       |                                 |                |
| Colloid intake, mL                              |  |                       |                                 |                |
| Total output, mL                                |  |                       |                                 |                |
| Urine output, mL                                |  |                       |                                 |                |
| Blood loss, mL                                  |  |                       |                                 |                |
| Fluid balance, mL                               |  |                       |                                 |                |
| Transfusion – no. (%)                           |  |                       |                                 |                |
| Packed red blood cells                          |  |                       |                                 |                |
| Fresh frozen plasma                             |  |                       |                                 |                |
| Platelets                                       |  |                       |                                 |                |
| Unplanned ICU/HDU admission – no. (%)           |  |                       |                                 |                |

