#### Randomization and blinding

Eligible patients are randomly allocated in a 1:1 ratio to the 'individualized high PEEP' or 'low PEEP' strategy. The allocation sequence is computer–generated by an independent investigator using permuted blocks of different block sizes, with a maximum block size of eight and stratified per center and BMI ( $\leq$  30 vs. > 30 kg/m^2). Randomization is performed by local investigators patient–by–patient employing a dedicated, password protected, SSL–encrypted website.

At each site, at least two investigators are involved with the study. One investigator randomizes the patients immediately before surgery and is responsible for the trial intervention and data collection. A second investigator remains blinded for the randomization and is responsible for postoperative data

collection. The surgeon and patient are kept blind to the allocated ventilation strategy. Since PEEP can be adjusted at any time point upon the surgeons' request or because of concerns about patient's safety, and since patients do not profit from knowing to which group they are allocated to, unblinding is not applicable.

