#### Adherence to study interventions and ventilatory variables

Surgical and perioperative characteristics will be reported (**Tables 4** and **5**). Ventilatory variables and vital signs will be reported after intubation, one hour, and in the last hour of surgery and compared between the two groups. Absolute differences between groups will be calculated using median regression for continuous variables (reported as median difference) and generalized linear models with binomial distribution and an identity link for binary variables (reported as difference in percentages). Plots comparing ventilatory variables and vital signs among the groups during the first three hours of surgery and in the last hour will be constructed (presenting the data as mean and 95% confidence interval in each time point).

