| eFigure 1     | Characteristics of the Intervention
A, Line plot reporting the mean and 95% confidence interval of the driving pressure after intubation, after recruitment maneuver, during first and second hour of surgery and at the last hour by treatment group.
B, Bar plot reporting the mean difference in driving pressure between groups after intubation, after recruitment maneuver, during first and second hour of surgery and at the last hour.
C, Bar plot showing the titrated level of PEEP in the individualized high PEEP group.
D, Line plot showing the plateau pressure and driving pressure according to PEEP levels during the PEEP titration maneuver in the individualized high PEEP. |
| eFigure 2     | Level of PEEP in the Study Population
Histogram reporting the most used level of PEEP during the first five hours of the surgical procedure by treatment group.  |
| eFigure 3     | Tidal Volume, PEEP, Peak Pressure, Plateau Pressure, FiO 2 and SpO 2 During Surgery
Line graph reporting the mean and 95% confidence interval of the variables after intubation, after recruitment maneuver, during first and second hour of surgery and at the last
hour by treatment group.   |
| eFigure 4     | VAS Pain, Respiratory Rate, SpO 2 and Mean Arterial Pressure During the First Five Days of Follow-Up
Line graph reporting the mean and 95% confidence interval of the variables in the first five days of follow-up by treatment group.   |
| eFigure 5     | Patient Status in the First Five Days of Follow-Up  |

|           | Transition plot showing the status of the patients in the first five days of follow-up.   |
|-----------|---|
| eFigure 6 | Confidence Distribution for the Primary Outcome
Confidence distribution of the estimated absolute difference of the primary outcome of Individualized High PEEP versus Low PEEP constructed using a normal approximation.
A, The full confidence distribution of the estimated absolute difference, with the dashed vertical line indicating the median value and the area highlighted in tan indicating the
95% confidence interval. The orange area is related to an absolute difference greater than 0 (i.e., the intervention is associated with higher incidence of PPC vs standard care).
The dotted line at an absolute difference of 0 indicates no treatment effect. The figure demonstrates that the confidence probability that Individualized High PEEP is associated |

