# Table 3 (Table 1) – Baseline Characteristics of the Included Patients

|  | Individualized High PEEP
(n = XXX) | Low PEEP
(n = XXX) |
|--|---------------------------------------|-----------------------|
| Systolic blood pressure, mmHg                  |                                       |                       |
| Mean arterial pressure, mmHg                   |                                       |                       |
| Respiratory rate, breaths/min                  |                                       |                       |
| Temperature, °C                                |                                       |                       |
| SpO 2 , %                           |                                       |                       |
| SpO 2 < 96% - no. (%)               |                                       |                       |
| Preoperative chest X-ray – no. (%)             |                                       |                       |
| Infiltrates                                    |                                       |                       |
| Pleural effusion                               |                                       |                       |
| Atelectasis                                    |                                       |                       |
| Preoperative laboratory                        |                                       |                       |
| Hemoglobin, g/dL                               |                                       |                       |
| Creatinine, mg/dL                              |                                       |                       |
| Data are median (quartile 25th - quartile 75th | ) or N / total (%)                    |                       |

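### Intraoperative and daily vital signs are compared without using the preoperative values already collected, which costs precision, and the plan does not say whether the after-intubation reading precedes any difference between arms

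*SAP*

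**What the plan says.** Under Adherence to study interventions and ventilatory variables, the SAP states: "Ventilatory variables and vital signs will be reported after intubation, one hour, and in the last hour of surgery and compared between the two groups". The method follows: "Absolute differences between groups will be calculated using median regression for continuous variables (reported as median difference"). No covariate is named. Other daily characteristics repeats the same method for the daily variables, again without a covariate.

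"Table 4 (Table 2) – Ventilation and Intraoperative Characteristics" has columns for the absolute difference with 95% CI and for a p value. They stand over the rows labelled "After intubation" and over the first-hour and last-hour rows alike, and no row is exempted.

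The baseline table (Table 3) lists preoperative vital signs, including "Mean arterial pressure, mmHg", SpO2 and respiratory rate, and has no p value column. SpO2 and mean arterial pressure return in Table 4. All three return in the daily assessment (Table 6 and eFigure 4).

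On timing, the eFigure 1 legend in the list of proposed tables and figures gives the order of readings as "driving pressure after intubation, after recruitment maneuver, during first and second hour of surgery and at the last hour by treatment group". Randomization and blinding states: "One investigator randomizes the patients immediately before surgery and is responsible for the trial intervention and data collection".

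**The concern.** A patient's preoperative blood pressure, saturation and respiratory rate can be expected to predict later values of the same variable. Leaving them out of the model gives up precision that costs nothing to obtain, because the values are already in the database. The wider intervals affect how clearly the paper can describe the haemodynamic and oxygenation consequences of the two strategies.

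A second question concerns the first row of each block in Table 4. If nothing distinguishes the arms at that reading, its p value tests only the play of chance, which the SAP avoids in Table 3. If something does distinguish them, the p value describes how patients were handled. The plan does not say which applies, and Table 4 is intended as Table 2 of the main paper.

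**Working it through.** The SAP gives no figure for this point. Its sample size (1,468) concerns the primary outcome and does not enter the check.

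**Inputs from the SAP**
- Model: median regression, no covariates (the two sections named above).
- Preoperative counterparts: respiratory rate, SpO2 and mean arterial pressure in Table 3. Of the Table 4 variables whose labels can be read (FiO2, SpO2, etCO2, mean arterial pressure), two have a preoperative counterpart. All three do in Table 6.
- After-intubation rows in Table 4: 10. These are the four variables just named plus six blocks whose labels were lost when the text was read from the PDF.
- Significance level: 0.05 two-sided, stated for the primary and secondary outcomes. It is assumed for Table 4, where none is given. The Holm–Bonferroni correction covers the 17 secondary outcomes only.

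**Assumed input**
- The correlation r between the preoperative and the later value. The SAP gives none; the range taken is 0.3 to 0.7.

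**Precision forgone.** Adjusting for a covariate with correlation r multiplies the variance of the treatment difference by 1 − r². The interval therefore narrows by 1 − √(1 − r²), and the equivalent sample-size factor is 1/(1 − r²).

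| r | 1 − r² | √(1 − r²) | Interval narrower by | 1/(1 − r²) |
|---|---|---|---|---|
| 0.3 | 0.91 | 0.954 | 5% | 1.10 |
| 0.5 | 0.75 | 0.866 | 13% | 1.33 |
| 0.7 | 0.51 | 0.714 | 29% | 1.96 |

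The formula is the least-squares result and carries over to median regression under bivariate normality. A small simulation of median regression with normal data (400 patients, 250 repetitions) gave ratios of adjusted to unadjusted standard error of 0.93, 0.90 and 0.67 at the three correlations, against 0.95, 0.87 and 0.71 from the formula. The agreement is rough.

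**After-intubation p values.** This step applies only if the arms are managed alike up to that reading. Ten null tests at 0.05 then give 10 × 0.05 = 0.5 expected false positives. If the tests were independent, the probability of at least one would be 1 − 0.95¹⁰ = 0.40. The variables are linked, so the true figure is probably lower.

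**Is that condition met?** The eFigure 1 and eFigure 3 legends list the reading before the recruitment maneuver, which suggests that PEEP has not yet been individualized. But patients are randomized before surgery, and the investigator who randomizes also handles the intervention and data collection. No sentence says that settings are common to both arms until the recruitment maneuver. The legends give an order, not a rule of conduct, so the condition is plausible but not established.

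**The case against.** The strongest reply is that nothing here is an error. Unadjusted comparisons of randomized groups are unbiased, and their intervals already allow for chance imbalance. The variables concerned describe process and daily course. This stands: the gain is in efficiency, not validity.

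A reader might infer that every difference at the after-intubation reading is chance, and that this reading should be the covariate for later ones. The SAP does not support that. The reading is post-randomization, is taken by someone who knows the allocation, and is placed before the recruitment maneuver only by figure legends. If settings already differ, adjusting for it could remove part of the contrast between arms. Choosing the covariate site by site, according to whether settings appear to differ, would be a worse rule than the present one. Comparing arms at that point may also be a legitimate adherence check, which the section heading suggests.

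A reader might also take the 40% as the trial's false-positive rate for these rows. It needs both the unproven condition and independence among variables that are partly linked.

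The gain is uncertain too. SpO2 is bounded, the correlations are assumed, and those between a preoperative value and a reading under anaesthesia may differ from those with a value days later. Adjustment in median regression yields a conditional median difference, which need not equal the difference between the printed medians. These limits are accepted. They reduce the expected benefit but do not remove the case for using a preoperative covariate.

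**Conclusion.** The point holds as one of precision and clarity. The daily comparisons of respiratory rate, SpO2 and mean arterial pressure, and the first-hour and last-hour comparisons of SpO2 and mean arterial pressure, leave a measured preoperative predictor unused. The intervals could be narrower by roughly 5% to 29% for correlations of 0.3 to 0.7. That range is assumed, and the ratio is approximate for median regression.

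The status of the after-intubation rows depends on something the plan leaves unstated. They are a test of chance if the arms are managed alike until the recruitment maneuver, and a process check if they are not. Nothing here affects the primary outcome, the secondary outcomes, their error control or the sample size. The importance is modest and the remedy is cheap.

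**What to change.** - **Other daily characteristics:** add the patient's preoperative value as a covariate in the daily comparisons of respiratory rate, SpO2 and mean arterial pressure.
- **Adherence to study interventions and ventilatory variables:** add the preoperative value as a covariate in the first-hour and last-hour comparisons of SpO2 and mean arterial pressure.
- **Tables 4 and 6:** keep unadjusted medians and quartiles as the displayed summaries, and label the difference for these variables as adjusted (a conditional median difference).
- **After-intubation reading:** state whether the arms are managed alike until the recruitment maneuver. If so, show the ten rows descriptively without p values; the reading may then also serve as a covariate. If not, label the rows a process check and do not adjust for them.
- **Missing preoperative values:** state how they are handled in these models, so that patients are not lost by default.

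The cost is a few sentences and one covariate per affected model, with no new data. The price is a difference that no longer matches the raw medians beside it exactly, which the label makes clear.

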## Table 4 (Table 2) – Ventilation and Intraoperative Characteristics

Data are median (quartile 25th - quartile 75th) or N / total (%).

Abbreviation:  $\Delta P$  is driving pressure, PEEP is positive end-expiratory pressure, PBW is predicted body weight, FiO2 is inspired fraction of oxygen, SpO2 is pulse oximetry, etCO2 is end-tidal carbon dioxide, ICU is intensive care unit, HDU is high dependency unit.

|  | Individualized
High PEEP
(n = XXX) | Low PEEP
( n = XXX) | Absolute Difference
(95% Cl) | p value |
|--|--|-------------------------------|---------------------------------|---------|
| Fluids   | (11 1004)                                |                               |                                 |         |
| Total intake, mL                                     |  |                               |                                 |         |
| Crystalloids – no. (%)                               |  |                               |                                 |         |
| Cumulative intake, mL                                |  |                               |                                 |         |
| Colloid – no. (%)                                    |  |                               |                                 |         |
| Cumulative intake, mL                                |  |                               |                                 |         |
| Total output, mL                                     |  |                               |                                 |         |
| Urine output – no. (%)                               |  |                               |                                 |         |
| Cumulative output, mL                                |  |                               |                                 |         |
| Blood loss – no. (%)                                 |  |                               |                                 |         |
| Cumulative loses, mL                                 |  |                               |                                 |         |
| Fluid balance, mL                                    |  |                               |                                 |         |
| Vasopressors   |  |                               |                                 |         |
| Dobutamine – no. (%)                                 |  |                               |                                 |         |
| Cumulative dose, mg                                  |  |                               |                                 |         |
| Dopamine – no. (%)                                   |  |                               |                                 |         |
| Adrenaline – no. (%)                                 |  |                               |                                 |         |
| Cumulative dose, mg                                  |  |                               |                                 |         |
| Ephedrine – no. (%)                                  |  |                               |                                 |         |
| Cumulative dose, mg                                  |  |                               |                                 |         |
| Noradrenaline – no. (%)                              |  |                               |                                 |         |
| Cumulative dose, mg                                  |  |                               |                                 |         |
| Phenylephrine – no. (%)                              |  |                               |                                 |         |
| Cumulative dose, mg                                  |  |                               |                                 |         |
| Transfusion  |  |                               |                                 |         |
| Packed red blood cells – no. (%)                     |  |                               |                                 |         |
| Cumulative amount, mL                                |  |                               |                                 |         |
| Fresh frozen plasma – no. (%)                        |  |                               |                                 |         |
| Cumulative amount, mL                                |  |                               |                                 |         |
| Platelets – no. (%)                                  |  |                               |                                 |         |
| Cumulative amount, mL                                |                                   |                               | -                               | -       |
| Data are median (quartile 25th - quartile 75th) or N | / total (%).                             |                               |                                 |         |

# Table 5 (eTable 2) – Additional Intraoperative Characteristics

Data are median (quartile 25th - quartile 75th) or N / total (%) Abbreviations: PEEP is positive end-expiratory pressure.

|  | Individualized
High PEEP
(n = XXX) | Low PEEP
(n = XXX) | Absolute Difference
(95% Cl) | p value |
|--|--|-----------------------|---------------------------------|----------------|
| Day 1                                      |  |                       |                                 |                |
| Patients in hospital $-$ no (%)            |  |                       |                                 |                |
| Admission to $ICII = no. (\%)$             |  |                       |                                 |                |
| Mechanical ventilation $-$ no. (%)         |  |                       |                                 |                |
| Invasive                                   |  |                       |                                 |                |
|  |  |                       |                                 |                |
| Physioliterapy $-10.(\%)$                  |  |                       |                                 |                |
| Renai replacement therapy $-10.(\%)$       |  |                       |                                 |                |
| VAS palli
Respiratory rate, breaths/min |  |                       |                                 |                |
|  |  |                       |                                 |                |
| SpO 2 , %                       |  |                       |                                 |                |
| Day 2                                      |  |                       |                                 |                |
| Day 2
Patients in hospital $-$ no. (%)  |  |                       |                                 |                |
| Admission to $ICII = no. (\%)$             |  |                       |                                 |                |
| Mechanical ventilation $-$ no. (%)         |  |                       |                                 |                |
| Invasive                                   |  |                       |                                 |                |
| Non-invasive                               |  |                       |                                 |                |
| Physiotherapy – no. (%)                    |  |                       |                                 |                |
| Renal replacement therapy $-$ no. (%)      |  |                       |                                 |                |
| VAS pain                                   |  |                       |                                 |                |
| Respiratory rate, breaths/min              |  |                       |                                 |                |
| SpO 2 , %                       |  |                       |                                 |                |
| Mean arterial pressure, mmHg               |  |                       |                                 |                |
| Day 3                                      |  |                       |                                 |                |
| Patients in hospital – no. (%)             |  |                       |                                 |                |
| Admission to ICU – no. (%)                 |  |                       |                                 |                |
| Mechanical ventilation – no. (%)           |  |                       |                                 |                |
| Invasive                                   |  |                       |                                 |                |
| Non-invasive                               |  |                       |                                 |                |
| Physiotherapy – no. (%)                    |  |                       |                                 |                |
| Renal replacement therapy – no. (%)        |  |                       |                                 |                |
| VAS pain                                   |  |                       |                                 |                |
| Respiratory rate, breaths/min              |  |                       |                                 |                |
| SpO 2 , %                       |  |                       |                                 |                |
| Mean arterial pressure, mmHg               |  |                       |                                 |                |
| Day 4                                      |  |                       |                                 |                |
| Patients in hospital – no. (%)             |  |                       |                                 |                |
| Admission to ICU – no. (%)                 |  |                       |                                 |                |
| Mechanical ventilation – no. (%)           |  |                       |                                 |                |
| Invasive                                   |  |                       |                                 |                |

